While core elements of this program are transferable—such as its structured guide—clinical use remains low. For example, even after training, clinicians at Penn Medicine document SICs for fewer than 5% of patients with advanced cancer.²² There is critical need to develop, test, and disseminate strategies to improve the frequency of SICs.

Implementation strategies informed by behavioral economics are ideally suited to address this problem, which is fundamentally one of clinician and patient behavior change. By intentionally modifying the way choices are framed, behavioral nudges can lead to desirable changes in clinician behavior while preserving clinician choice.²²⁻²⁵ Our preliminary work demonstrates the effectiveness of an implementation strategy focusing on a clinician nudge, consisting of performance feedback and targeted text messages identifying patients at high risk of mortality based on a validated machine learning prognostic algorithm.²⁶ This strategy led to a threefold increase in SIC documentation for high-risk patients, equitably across racial/ethnic minority subgroups, and is now in routine use across Penn Medicine practice sites. However, clinicians still did not document SICs for over half of patients, illustrating the limitations of a clinician-directed implementation strategy alone.²⁶ The purpose of this study is to test behavioral economics-informed multilevel implementation strategies to prompt clinicians and patients to engage in early SICs. This study will expand on these preliminary findings to evaluate the synergy between clinician- and patient-directed nudges to increase SIC documentation.

OBJECTIVES:

Aim 1: Conduct a pragmatic four-arm randomized controlled trial to test the effectiveness of nudges to clinicians, nudges to patients, or nudges to both in increasing the frequency and timeliness of SIC documentation, compared to usual practice.

1. Primary objective:

Test the effect of nudges to clinicians, nudges to patients, or nudges to both, compared to usual practice, on SIC documentation, among high-risk patients.

2. Secondary objectives:

Test the effect of nudges to clinicians, nudges to patients, or nudges to both, compared to usual practice, on the following secondary outcomes:

- a) SIC documentation, among all patients
- b) Palliative care referral, among high-risk patients

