4. Early Withdrawal of Subjects:

We are requesting a waiver of informed consent, so the option to withdraw early from this study is not applicable.

5. Vulnerable Populations:

Children, pregnant women, fetuses, neonates, or prisoners are not being targeted in this research study.

6. Populations vulnerable to undue influence or coercion:

We will not be targeting participants who are likely to be vulnerable to undue influence or coercion.

STUDY DESIGN:

1. Study design:

We will conduct a pragmatic four-arm randomized controlled trial to test the effectiveness of nudges to clinicians, nudges to patients, or nudges to both in promoting SIC documentation, compared to usual practice. We will independently randomize eligible clinicians and patients using a 2x2 factorial design. Clinicians will be randomized to receive a nudge consisting of targeted text messages identifying patients at high risk of predicted 6-month mortality based on a validated machine learning prognostic algorithm and performance feedback compared to peers (“clinician peer comparison”), versus usual practice. Patients will be randomized to receive a nudge consisting of a normalizing message prompting patients to complete an electronic questionnaire designed to prime patients towards having an SIC (“patient priming”), versus usual practice. This design will thus lead to four independent study groups: (1) nudge to both clinician and patient, (2) nudge to clinician only, (3) nudge to patient only, and (4) usual practice, as depicted below.

Figure: 2x2 factorial design

		Patient	
		Nudge	No nudge
Clinician	Nudge	Arm 1: Nudge to clinician and patient (peer comparison & patient priming)	Arm 2: Nudge to clinician only (clinician peer comparison)
	No nudge	Arm 3: Nudge to patient only (patient priming)	Arm 4: Usual practice (active control)

2. Study Duration:

The study duration will be approximately 6 months per participant, defined by an initial index clinical encounter (marking the beginning of the nudge exposure period) and followed by a 6-month follow-up period over which outcomes will be ascertained. We will employ rapid cycle approaches (RCA) prior to clinical trial enrollment to optimize implementation strategies.

METHODS:

1. Study Instruments:

Any study instruments will be submitted to the IRB as a modification prior to use.

2. Administration of Surveys and/or Process:

Any surveys will be submitted to the IRB as a modification prior to use.

3. Data Management:

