Usual practice. Usual practice will consist of targeted text messages identifying patients at high risk of mortality based on a validated machine learning prognostic algorithm, as well as clinician-directed performance feedback (WITHOUT peer comparison), thereby serving as an active control arm.

We will use RCA to optimize implementation strategies to ensure face validity and maximum effect. We will focus on optimizing content, messaging, and design. RCA procedures will involve design meetings with study team, discussions with administrators and clinicians who are members of our Implementation Lab, as well as piloting of nudges with clinicians and patients to elicit feedback.

2. Data Collection:

The electronic medical record and other Penn Medicine secondary databases will be used to collect information on practices, clinicians, and patients. These systems collect this information as part of routine clinical care. We will also collect data from the U.S. Census via publicly available datasets.

Aim 1

The primary outcome is SIC documentation among high-risk patients. This will be measured at the patient level as a binary outcome, ascertained over the 6-month period following the index outpatient clinical encounter. The electronic medical record has an Advanced Care Planning (ACP) section in which ACP notes are documented. Any note documented in this section will be classified as an ACP, and only the subset of notes that include a preformatted SIC template will be classified as a SIC.

The secondary outcomes will each be measured at the patient level as a binary outcome, ascertained over the 6-month period following the index outpatient clinical encounter:

- SIC documentation, among all patients
- Palliative care referral, among high-risk patients
- Aggressive end-of-life care (any of the following three criteria: chemotherapy within 14 days before death, hospitalization within 30 days before death, or admission to hospice 3 days or less before death), among high-risk patients who die

Aim 2

Aim 2 measures, collected through the electronic medical record and using publically available U.S. Census data, will include:

- *Patient-level data*: age, sex, race/ethnicity, cancer type, cancer stage, health insurance (e.g., Medicare, Medicaid, commercial);
- *Clinician-level data*: years in practice and patient panel size;
- *Practice-level data*: setting (community vs. hospital-based), urban vs. non-urban location, and health insurance mix;

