- *Ecologic-level data* linked at the patient- and practice-level, including median income and educational attainment.

Aim 3

Aim 3 data collection will additionally consist of patient-reported content obtained during the course of the study in response to the SIC priming questionnaire, among 1,166 participants randomized to the patient nudge study arm who completed the SIC priming questionnaire (Appendix 2).

3. Genetic Testing:

Not applicable

4. Use of Deception:

Not applicable

5. Statistical Analysis:

Aim 1

The primary outcome will be modeled in a time-to-event analysis using a Cox proportional hazards model, with cluster-correlated robust standard errors to account for clustering by clinical site. SIC documentation, as defined above, will serve as the primary event outcome. Days between the index clinical encounter (at which the nudge exposure period begins) and SIC documentation will serve as the time variable. The design is a 2x2 factorial, which breaks down into 4 study arms (defined by clinician cluster and patient randomization at the index clinical encounter): nudge to clinician only, nudge to patient only, nudge to both, or usual practice. Cox regression will estimate hazard ratios for the main effects (Aim 1) and a ratio of hazard ratios for the interaction term (Aim 2). Significance will be determined using the z-score corresponding to each of the estimated effects, using a two sided type 1 error of 5%. All enrolled patients will be included in the intention-to-treat analysis, and subjects will be censored at the time of last follow-up or death, should they

not have been observed to have a documented SIC during the follow-up period. Covariates will be assessed across study arms and included in the Cox model if unbalanced across arms.

We will use our fitted Cox model to generate predicted probabilities of SIC documentation within 6 months, via marginal standardization, as well as median time to documented SIC across arms. The functional form of the model will be checked using cumulative martingale residuals, and the proportional hazards assumption will be checked using scaled Schoenfeld residuals.

The secondary outcomes will be similarly modeled. All hypothesis tests will use a two-sided alpha of 0.05 as the threshold for statistical significance.

Aim 2

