We are seeking to detect the main effects of nudges and their interaction with at least 80% power using a two-sided alpha of 0.05. We anticipate enrolling 66 physician-APP clusters who will together care for an estimated 5,500 high-risk patients over the study period, yielding approximately 83 high-risk patients per cluster on average. We have generated power calculations using various patient enrollment and cluster correlation assumptions as below. We calculated power by simulation, generating exponential time to event under a variety of assumptions. Patients are clustered within clinician units. Higher correlation within cluster will generally help with power for within-cluster comparisons, but degrade power for between-cluster comparisons. Within cluster correlation was imposed by drawing correlated Normally-distributed random numbers, transformed to exponential using copula methods.

Patients per Cluster	Within Cluster Correlation	Detectable True HR of Effect (Power)		
		Provider nudge	Patient nudge	Interaction

70	0.1	1.6 (86%)	1.25 (84%)	1.6 (80%)
70	0.3	2.0 (85%)	1.3 (90%)	1.8 (91%)
90	0.1	1.6 (91%)	1.25 (86%)	1.6 (85%)
90	0.3	2.0 (86%)	1.25 (84%)	1.6 (83%)

Assuming conservatively that we enroll 70 patients per cluster with a cluster correlation of 0.1, we will have >80% power to detect a true hazard ratio of effect of HR 1.6 for the provider nudge, HR 1.25 for the patient nudge, and HRR 1.6 for the interaction. Assuming 70 patients per cluster and a cluster correlation of 0.3, we will have >80% power to detect a true hazard ratio of effect of HR 2.0 for the provider nudge, HR 1.3 for the patient nudge, and HRR 1.8 for the interaction. These estimates improve slightly if we assume enrollment of 90 patients per cluster, allowing us to detect similar effect sizes with more power, as shown in the Table above.

RISK/BENEFIT ASSESSMENT:

1. Risks:

There are minimal risks to participants in this trial. There is a risk of breach of data and confidentiality, however we described the precautions in place to securely manage this data in the Data Management section of this protocol. As noted above, substantial data demonstrates that ACPs improve patient goal-concordant care without any identified harms (despite concerns that ACPs may increase psychosocial distress, the opposite has been found), so the negative impact on patients is minimal.

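### The Cox-based 6-month SIC probabilities and medians treat death as censoring and so overstate how many patients have a documented SIC; the hazard-ratio test remains valid.

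*Combined protocol and SAP*

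**What the plan says.** Under Study Procedures, 2. Data Collection, Aim 1, the primary outcome is SIC documentation in high-risk patients: "This will be measured at the patient level as a binary outcome, ascertained over the 6-month period following the index outpatient clinical encounter".

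Under Study Procedures, 5. Statistical Analysis, Aim 1, this outcome is analysed by Cox regression on days from the index encounter. For patients without an SIC, "subjects will be censored at the time of last follow-up or death". On testing, "Significance will be determined using the z-score corresponding to each of the estimated effects". The fitted model is also used to "generate predicted probabilities of SIC documentation within 6 months, via marginal standardization, as well as median time to documented SIC across arms". For the other endpoints, "The secondary outcomes will be similarly modeled".

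Deaths are expected. The Study Design section describes the clinician messages as "identifying patients at high risk of predicted 6-month mortality", and one secondary outcome is restricted to high-risk patients who die. The plan names no competing-risk method. It does not say how a patient who dies without an SIC counts in the binary outcome, and it does not present the predicted probabilities as hypothetical.

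**The concern.** A patient who dies without an SIC can never have one. A Cox model that censors at death answers a legitimate question: the rate of SIC documentation among patients still alive and without one. Converting that rate to a 6-month probability as 1 − exp(−cumulative hazard) treats patients who died as if they would have gone on to have SICs at the rate of the survivors. Marginal standardization averages these predictions over covariates and does not correct them.

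At stake are the numbers most readers will use: the SIC percentage in each arm, the differences between arms, and the median time. They would not describe the stated binary outcome, and they would disagree with a simple count from the same data.

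The median carries the same defect, since the death-censored curve can cross 50% when fewer than half of patients ever have an SIC. It may also not be reached in some arms. The introductory text says of the earlier clinician strategy that "clinicians still did not document SICs for over half of patients".

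**Working it through.** **Inputs.** The plan states no figure for this quantity, so there is none to reproduce. Two inputs are assumed:
- Net 6-month mortality: 5% to 50%, unaffected by having an SIC.
- Cox-based control SIC probability: 15% or 30%.

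The effect sizes are from Power and Sample Size: "HR 1.6 for the provider nudge, HR 1.25 for the patient nudge", and HR 2.0 for the provider nudge at within-cluster correlation 0.3. A patient who dies without an SIC is counted as having none.

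**Formulas.** Let L = −ln(1 − Cox probability) and M = −ln(1 − mortality), the 6-month cumulative hazards of SIC and death.
- Plan's prediction: 1 − exp(−L).
- Proportion with an SIC, constant hazards: L/(L+M) × [1 − exp(−(L+M))].
- Front-loaded version: the same formula in two pieces. Month 1 carries 0.5L and M/6; months 2–6 carry 0.5L and 5M/6 and apply to those still at risk.
- Treated-arm Cox probability: 1 − (1 − control)^HR.

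**Worked case: Cox 30%, mortality 30%.** L = M = 0.3567.
- Constant hazards: 0.5 × (1 − exp(−0.7133)) = 0.5 × 0.51 = 25.5%.
- Front-loaded: month 1 gives 0.75 × (1 − exp(−0.2378)) = 0.1587, with 0.7884 still at risk. Later months give 0.7884 × 0.375 × (1 − exp(−0.4756)) = 0.1119. The total is 27.1%.

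**Proportion of patients with an SIC (%)**

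| Mortality | Cox 15%, constant | Cox 15%, front-loaded | Cox 30%, constant | Cox 30%, front-loaded |
|---|---|---|---|---|
| 5% | 14.6 | 14.8 | 29.3 | 29.5 |
| 10% | 14.3 | 14.5 | 28.6 | 29.1 |
| 20% | 13.5 | 14.0 | 27.1 | 28.1 |
| 30% | 12.7 | 13.5 | 25.5 | 27.1 |
| 50% | 10.9 | 12.3 | 22.1 | 24.8 |

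The relative overstatement is about 2–37% with constant hazards and 2–22% when front-loaded.

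**Arm differences in points** (equal mortality in both arms, ranges for 5% to 50% mortality)

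| Control, HR | Cox-based | Actual, constant | Actual, front-loaded |
|---|---|---|---|
| 15%, 1.25 | 3.4 | 3.3 to 2.5 | 3.3 to 2.8 |
| 15%, 1.6 | 7.9 | 7.7 to 5.8 | 7.8 to 6.5 |
| 30%, 1.6 | 13.5 | 13.2 to 10.3 | 13.3 to 11.5 |

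**Median.** A 30% control with HR 2.0 gives a Cox probability of 1 − 0.7² = 51%, so a median would be reported. With constant hazards, 49.9% (5% mortality) down to 38.3% (50% mortality) of patients have an SIC.

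**Simulation check.** A Cox model was fitted to 4,620 independent patients (66 × 70), with a 30% control and true HR 1.25, over 300 replicates.
- No deaths: predicted 30.0% and 36.0% by arm, matching the observed proportions.
- 30% mortality: predicted 30.05% and 35.95%, observed 25.55% and 30.63%. The estimated HR stayed at 1.25.
- Equal SIC hazards in both arms (1,000 replicates per setting): the HR test rejected in 4.1–4.8% of replicates, including when mortality differed by arm (30% vs 20%, 45% vs 30%).

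**The case against.** Censoring at death is standard for a cause-specific hazard ratio, and significance in this plan rests on that ratio. The predicted probabilities are descriptive, and the plan does not forbid also reporting the observed proportion. The large discrepancies depend on mortality near 50%, which the documents do not support in particular. At 5–20% mortality with constant hazards, the overstatement is 0.4–1.5 points on a Cox 15% and 0.7–2.9 on a Cox 30%. Front-loading is plausible because the patient nudge goes out before the index visit, and it shrinks the gap. Ratios barely move: for a 15% control and HR 1.25, the risk ratio is 1.226 by Cox and 1.226–1.228 by cumulative incidence. The median example is borderline: front-loaded at 5% mortality, 50.3% of patients have an SIC, so no contradiction arises.

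All of this stands as a limit on size, and two further qualifications are fair. First, the two figures coincide if every death without an SIC falls after the last SIC, which is unrealistic in about 5,500 high-risk patients. Second, the test remains valid, but it is not untouched by deaths:
- At an assumed 30% mortality, 15% control and HR 1.25, SIC events fell from 771 to 650 and simulated power from about 86% to 81%.
- When a shared frailty linked SIC and death and mortality differed by arm (45% vs 30%), rejection with no direct effect on SIC rose to 14.6%. With equal mortality it was 6.2%. Nothing in the documents suggests that the nudges change survival.

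None of this makes the death-censored probability a correct estimate of the stated outcome.

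**Conclusion.** The concern holds. Followed as written, the plan would report SIC percentages, arm differences and medians for a hypothetical cohort without deaths, and the error in the percentages runs upward. The size cannot be fixed from the documents. Under the assumed ranges it goes from negligible (0.4 points on a Cox 15% at 5% mortality) to material (7.9 points on a Cox 30% at 50% mortality), and less if SICs cluster early. These figures rest on the assumed mortality and SIC rates, on a death hazard unaffected by SIC and, for the arm differences, on equal mortality in both arms.

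This is a defect in the absolute effects, not in the primary test. The cause-specific hazard ratios and z-scores can stand. It should be corrected before analysis because absolute rates are what a health system would use to judge the nudges.

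**What to change.** - Keep the cause-specific Cox hazard ratio and its z-test.
- Report absolute SIC probabilities and risk differences as 6-month cumulative incidence with death as a competing event. Use Aalen-Johansen, or standardise from cause-specific Cox models for SIC and for death. If follow-up is complete to 6 months or death, the observed 6-month proportion can be used instead. Use intervals that account for clustering.
- Give cumulative incidence at fixed times, for example 1, 3 and 6 months, in place of or beside the median.
- If the Cox-based probabilities are kept, label them as probabilities in the absence of death.
- Apply the same to SIC among all patients and to palliative care referral.
- State how a patient who dies without an SIC counts in the binary outcome.

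The cost is a few sentences in the plan and slightly more programming, since death dates are already needed for the censoring rule. The reported rates and differences will be lower, though only slightly if mortality is low.

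### Median time to a documented SIC is the only planned timing summary in days, and usual practice will probably not reach it within 6 months

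*Combined protocol and SAP*

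**What the plan says.** Under Objectives, Aim 1 tests the nudges against usual practice "in increasing the frequency and timeliness of SIC documentation". Data Collection, Aim 1, defines the primary outcome as binary, "ascertained over the 6-month period following the index outpatient clinical encounter".

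Statistical Analysis, Aim 1, models days from the index encounter to SIC in a Cox model and censors at last follow-up or death. Its outputs are hazard ratios, standardized predicted probabilities of SIC within 6 months, "as well as median time to documented SIC across arms". No restricted mean or lower quantile is planned, and there is no rule for a median that is not reached.

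The opening summary, before the Objectives, gives the only background rates:

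- Even after training, "clinicians at Penn Medicine document SICs for fewer than 5% of patients with advanced cancer".
- On the earlier clinician strategy of performance feedback and targeted text messages: "This strategy led to a threefold increase in SIC documentation for high-risk patients".
- That strategy "is now in routine use across Penn Medicine practice sites".
- Under it, "clinicians still did not document SICs for over half of patients".

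Study Procedures describes usual practice as text messages identifying high-risk patients plus performance feedback without peer comparison, so it resembles the earlier strategy.

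**The concern.** A median can be read from a fitted curve only if the curve reaches 50% during follow-up. A Cox model gives no baseline hazard beyond the last observed time, so it cannot supply a later median without extrapolation.

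If fewer than half of usual-practice patients have an SIC by 6 months, the reference arm has no median. Every Aim 1 contrast is against usual practice, so a single unreached median removes all three differences in median time. The timeliness part of the aim would then have no comparison in days. A replacement measure would have to be chosen after the data were seen.

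**Working it through.** **Inputs.** Window: 6 months (Data Collection). Planned effects: provider HR 1.6, patient HR 1.25, HRR 1.6 for the interaction (Power and Sample Size, 70 patients per cluster, correlation 0.1); and 2.0, 1.3 and 1.8 at correlation 0.3. The usual-practice 6-month SIC probability, p0, is not stated, so it is varied here.

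**1. What the power table implies about p0.** The table gives no event rate and cannot be reproduced directly, but it can be back-solved.

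- Patient main effect: D = 4(z_a + z_b)² / ln(HR)². For HR 1.25 at 84% power, D = 4(1.960 + 0.994)² / 0.0498 ≈ 701 events among 66 × 70 = 4,620 patients, or 15%. The other three rows give about 13%, 12.5% and 12%.
- Interaction: D = 16(z_a + z_b)² / ln(HRR)². For HRR 1.6 at 80% power, D ≈ 568, or 12% of 4,620. The other rows give 10 to 11%.
- Simulation: 66 clusters of 70, Gaussian-copula exponential times with correlation 0.1, censoring at 6 months, cluster-robust exponential regression standing in for Cox, 300 runs per cell, run twice. At p0 = 10%, power for provider, patient and interaction is about 82%, 80 to 85% and 84 to 85%. The table states 86%, 84% and 80%. At p0 = 45%, all three are 99 to 100%.

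Across the table's rows, p0 of roughly 8 to 15% fits best. No single value fits every cell. The table does not look as if it was built on rates near 50%.

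**2. When each arm reaches a median.** With constant, proportional hazards, the 6-month probability in an arm is 1 − (1 − p0)^HR. Setting this to 50% gives p0 = 1 − 0.5^(1/HR).

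| Arm | HR | p0 needed |
|---|---|---|
| Usual practice | 1 | 50% |
| Patient nudge | 1.25 | 42.6% |
| Clinician nudge | 1.6 | 35.2% |
| Both, no interaction | 1.25 × 1.6 = 2.0 | 29.3% |
| Both, HRR 1.6 | 2.0 × 1.6 = 3.2 | 19.5% |
| Both, larger effects | 2.0 × 1.3 × 1.8 = 4.68 | 13.8% |

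**3. Illustrations.** Hazard λ = −ln(1 − p0)/6 per month; median = ln 2/(λ·HR). The order is usual practice, patient nudge, clinician nudge, both (HR 2.0).

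- p0 = 15% (an assumption: three times 5%): λ = 0.0271. Probabilities are 15, 18, 23 and 28%; implied medians are 25.6, 20.5, 16.0 and 12.8 months. With HR 3.2 the combined arm is at 41% (8.0 months); with HR 4.68 it is at 53% (5.5 months).
- p0 = 40%: λ = 0.0851. Probabilities are 40, 47, 56 and 64%; medians are 8.1, 6.5, 5.1 and 4.1 months. Two arms reach it.
- p0 = 45%: probabilities are 45, 53, 62 and 70%. Only usual practice misses.

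**4. Effect of censoring deaths.** The fitted curve estimates a net probability, 1 − exp(−l). The crude proportion is [l/(l + m)]·[1 − exp(−(l + m))], where l and m are the 6-month cumulative hazards of SIC and death, taken as independent and constant. Mortality is not given in the documents, so 20 to 40% at 6 months is assumed.

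- Crude 45% becomes 49.6%, 52.4% and 55.6% at 20, 30 and 40% mortality.
- Crude 40% becomes 49.6% at 40% mortality.
- Crude 15% becomes 22.5% even at 60% mortality.

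**5. A measure that exists in every arm.** Restricted mean SIC-free time to 6 months is [1 − exp(−6λ·HR)]/(λ·HR). At p0 = 15% it is 5.54, 5.43, 5.28 and 5.12 months; at 40% it is 4.70, 4.43, 4.10 and 3.76 months. All arms can be compared in both cases.

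**The case against.** The strongest reply is that little depends on the median. No test, power figure or decision uses it. The primary analysis already uses days to SIC, and its hazard ratios carry timing information. The standardized 6-month probabilities are absolute estimates by arm. The listed objectives contain no separate timing endpoint, and reporting a median as not reached is routine. Nothing in the plan says it will extrapolate. All of this stands and limits the severity.

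A reader might also infer three stronger claims that the documents do not support.

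- **That the usual-practice median cannot be reached.** The figure of over half undocumented has no stated time window and appears to be a crude proportion. The plan censors deaths, which raises the fitted curve, so a crude 40 to 49% could come out near or above 50%.
- **That most arms will miss their median.** This depends on the unstated p0. The 15% figure multiplies a rate in patients with advanced cancer by a ratio in high-risk patients, and it is an assumption. At 40%, two arms reach a median; at 45%, three do. Taking the combined HR as 2.0 also leaves out the planned interaction.
- **That no timing comparison would be possible.** The hazard ratios remain.

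The gap in the plan remains after this reply. An aim that names timeliness has one absolute measure in days, and that measure is likely to be missing in the arm that every contrast uses. A median reached only because deaths are censored would describe timing as if deaths had been removed.

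**Conclusion.** The concern holds as a probable failure of one planned summary. It does not affect the primary test. On the protocol's statement that over half of patients had no SIC under a strategy close to usual practice, the usual-practice median will probably not be reached within 6 months. Differences in median against it would then not be estimable.

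With HRs of 1.25, 1.6 and 2.0, no arm has a median if p0 is below 29.3%. One arm has it from there to 35.2%, two up to 42.6%, and three up to 50%. With the planned HRR of 1.6, the combined arm needs only 19.5%. The power table is consistent with p0 of roughly 8 to 15%, where only the combined arm under the largest planned effects could reach a median; that is a back-calculation and not a rate that the plan states.

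The conclusion assumes that usual practice performs roughly as the earlier strategy did and that the earlier figure is relevant to a 6-month window. The thresholds assume constant, proportional hazards. The hazard ratios and 6-month probabilities are unaffected.

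**What to change.** In Statistical Analysis, Aim 1, replace the median as the between-arm timing summary with restricted mean SIC-free days to 6 months per arm. Report between-arm differences with cluster-robust intervals. It can be computed as the area under the standardized SIC-free curve that the plan already needs for its 6-month probabilities. State that it inherits the model's handling of deaths. SIC proportions at 1 and 3 months can be added beside the 6-month figure.

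Report a median only for arms whose fitted curve crosses 50% within follow-up, and say that no extrapolation will be made. State the assumed usual-practice 6-month SIC rate next to the power table, so that readers can see which medians were expected to exist.

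The cost is a few sentences of text and a little more analysis and reporting. No new data are needed.
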